3.1 Types of Research Designs

Types of study designs: single-center, prospective cohort studies

Research Center: Drum Tower Hospital, Medical School of Nanjing University

Grouping method: non-randomized, open, enrolled according to patients' wishes

[figure not shown]
Sample size calculation basis and formula:

This study was a single-center prospective cohort study with two groups, the test group and the control group, and the serum albumin level of the study subjects was the primary endpoint outcome indicator observed. Based on the review of previous literature^[28] and reference to the results of the pretest, it was expected that the albumin level before LES intervention was 34.2 ± 3.9 g/L and the albumin level

after LES intervention was 37.5 ± 5.4 g/L, with a two-sided $\alpha=0.05$ and a degree of certainty of $1-\beta=90\%$. Using PASS15 software can be calculated to obtain $n=88$ cases. Based on the 1:1 grouping, 44 subjects were needed in each of the test and control groups, and assuming a 20% subject dropout rate, the final minimum number of subjects needed was 53 in each of the test and control groups, for a total of at least 106 subjects included.

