6.2 Nutrition indicators

Serum albumin (ALB), prealbumin (PA), total serum protein (TP), and transferrin were collected from subjects on day 1 of admission, day 6 postoperatively, 1 month postoperatively, 3 months postoperatively, and 6 months postoperatively.

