7.1 Nutritional indicators

Primary Efficacy Indicator:

Serum albumin (ALB), recording ALB data from patient biochemical tests.

Secondary efficacy indicators:

Prealbumin (PA), alanine aminotransferase (ALT), glutamate aminotransferase (AST), serum gamma-glutamyl transpeptidase (GGT), cholinesterase (CHE), total bilirubin (TBIL), and C-reactive protein (CRP) were recorded, and the corresponding data in the patient's biochemical tests were recorded;

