A data safety monitoring program will be established for clinical studies according to the level of risk. All adverse events will be recorded in detail, appropriately handled and followed up until properly resolved or stabilized, and serious adverse events and unintended events, etc., will be reported to the Ethics Committee, the competent authority, the sponsor, and the drug regulatory authority in a timely manner according to the regulations; the principal investigator will conduct a cumulative review of all adverse events on a regular basis, and convene a meeting of the investigators to assess the risks and benefits of the study, if necessary; the injuries or discomfort is no more likely and no greater in magnitude than that encountered in daily life or than that of a routine examination, and that data and safety monitoring can be accomplished by the principal investigator.

10. Statistical processing

应用 SPSS26.0 统计软件对临床数据进行描述性统计，符合正态分布的计量资料以均数±标

准差($\bar{x} \pm s$)表示, 组间采用 t 检验, 不符合正态分布的计量资料以中位数(四分位间距) [M(IQR)] 表示, 组间采用 Mann-Whitney U 检验。计数资料用百分比[n(%)]表示, 组间比较采用卡方检验, $P<0.05$ 为有显著性统计学意义。采用 STATA12.0 中的 Kaplan-Meier 法计算各组复发率及无复发生存期, log-rank 检验进行组间比较。SPSS26.0 statistical software was applied to carry out descriptive statistics of the clinical data, and the measurements that conformed to normal distribution were expressed as mean \pm standard deviation ($\bar{x} \pm s$), and t-test was used between the groups, and the measurements that did not conform to normal distribution were expressed as median (inter-quartile spacing) [M(IQR)], and Mann-Whitney U-test was used between the groups. Count data were expressed as percentages [n(%)], and the chi-square test was used for between-group comparisons, with $P<0.05$ considered statistically significant. The Kaplan-Meier method in STATA 12.0 was used to calculate the recurrence rate and recurrence-free survival in each group, and the log-rank test was used for between-group comparisons.

11. Ethical principles of clinical research

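### Albumin is measured five times with 20% dropout assumed, but the two-group tests make no use of earlier values, so later comparisons can be biased if dropout differs between groups

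*Combined protocol and SAP*

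**What the plan says.** Section 7.1 names the primary indicator as "Serum albumin (ALB), recording ALB data from patient biochemical tests", without a primary time point. Under section 6.2, albumin and the other nutritional indicators "were collected from subjects on day 1 of admission, day 6 postoperatively, 1 month postoperatively, 3 months postoperatively, and 6 months postoperatively".

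The sample-size text in section 3.1 arrives at 44 patients per group and then, "assuming a 20% subject dropout rate", raises this to 53 per group (106 in total). Dropout is not mentioned again as an analysis matter.

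The analysis is described three times: in the synopsis, under Data analysis in section 3.2, and in section 10. For normally distributed measures, "t-test was used between the groups"; for other continuous measures the test is Mann-Whitney. None of the three gives a repeated-measures model, adjustment for admission albumin, a missing-data rule, an analysis set or a sensitivity analysis.

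The second list of exclusions, section 4.4, applies after enrolment. Items 5 and 6 remove patients according to bedtime eating, with a different rule for each group, and item 7 removes those who withdraw voluntarily.

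**The concern.** A two-sample test of albumin at month 3 or 6 can include only patients who have a value at that visit. For a patient lost after month 1, the admission, day-6 and month-1 values contribute nothing to the month-6 comparison, although they are informative about the value that is missing.

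This matters if the patients lost differ from those who stay, and differ in another way in the other group. The design makes that plausible. Grouping is open and follows patients' wishes. After discharge the test group has a daily snack regimen, while controls continue support only if a doctor judges it necessary. The background section itself links reduced albumin synthesis and poor intake after hepatectomy to complications and poor prognosis. If low-albumin patients leave one group more readily than the other, the groups compared at month 6 are selected differently, and a difference can appear, shrink or reverse without any effect of the snack. Enrolling more patients makes the estimate more precise but leaves this bias unchanged.

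**Working it through.** **1. The plan's own figures (section 3.1).** The inputs are 34.2 (SD 3.9) and 37.5 (SD 5.4) g/L, two-sided 0.05, 90% power and 1:1 grouping. The difference is 37.5 − 34.2 = 3.3 g/L. The pooled SD is √[(3.9² + 5.4²)/2] = √[(15.21 + 29.16)/2] = 4.71 g/L. The unequal-variance t-test has power 0.894 at 43 per group and 0.901 at 44, so 44 per group (88) reproduces. The 53 reproduces as 44 × 1.2 = 52.8. A 20% loss from 53 leaves about 53 × 0.8 = 42 per group.

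**2. Assumptions that the documents do not give.** SD 4.71 g/L at each visit; correlation ρ between the earlier and the month-6 value of 0.4, 0.6 or 0.8; 20% dropout per group, governed by the earlier albumin value; no true effect. Month 6 is used as the illustration because no primary time point is named.

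**3. Formula.** Let z be the earlier albumin in SD units. If the mean of z among those who stay is s in one group and 0 in the other, the bias of the month-6 difference is s × ρ × 4.71.

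**4. Same dropout rule in both groups.** The two shifts cancel. Bias is about 0 and the type I error about 5%.

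**5. Graded dropout in one group, random in the other.** The odds of leaving double per SD lower albumin: p(z) = 1/[1 + exp(1.52 + 0.693z)], which averages 0.20. Numerical integration gives s = 0.129.

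**6. Extreme case.** All of the lowest 20% in one group leave, and the other group loses 20% at random. Then s = φ(−0.842)/0.8 = 0.280/0.8 = 0.35.

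| Scenario | ρ = 0.4 | ρ = 0.6 | ρ = 0.8 | Simulated type I error |
|---|---|---|---|---|
| Same in both groups | about 0 | about 0 | about 0 | about 5% |
| Graded, one group | 0.24 g/L | 0.36 g/L | 0.49 g/L | 5% to 8% |
| Extreme, one group | 0.66 g/L | 0.99 g/L | 1.32 g/L | 10% to 29% |

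Simulation with 53 per group agrees: 0.23 to 0.49 g/L graded, and 0.66 to 1.35 g/L extreme. Relative to the planned 3.3 g/L, the graded case is 7% to 15% (0.24/3.3 to 0.49/3.3) and the extreme case 20% to 40% (0.66/3.3 to 1.32/3.3). The sign reverses if the selected group is the control group.

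**7. A true effect present.** Suppose the effect grows evenly to 3.3 g/L at month 6, ρ is 0.5 to 0.7, and both groups follow the same dropout rule (log-odds slope 1 or 2 per SD of month-3 albumin, 20% lost overall). The effect itself changes who leaves, and the available-case difference averages 2.89 to 3.16 g/L. An estimate that uses the earlier values gives 3.28 to 3.31.

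**8. What the earlier values can and cannot correct.** When dropout depends on recorded albumin, an estimate using the earlier values has bias of about 0 in every scenario run. When dropout in one group depends on the unseen month-6 value (ρ 0.5 to 0.7), the available-case bias is about ±0.8 to ±1.25 g/L, and about ±0.3 to ±0.8 g/L remains after the earlier values are used.

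**The case against.** The strongest reply is that the bias is conditional and the documents do not show that its condition is met. They give no dropout mechanism, direction or between-visit correlation. With no true effect and matching dropout in the two groups, the available-case test is sound. With graded dropout in one group the type I error reaches at most about 8%. Comparing attenders at each visit is also an inference: the plan never says so, and it names no primary time point. Day 6 is early enough that dropout probably affects it little. All of this stands, and it limits the size of the point. It does not supply a method for the missing values, and the inference is close to forced, because a two-sample test with no missing-data rule can use only the values present.

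Three stronger readings are tempting and should not be drawn. A reader might infer that the month-6 result will favour the snack, with a type I error approaching 29%. That needs every lowest-albumin patient in the test group to leave while controls leave at random, and nothing in the documents says so. A reader might infer that dropouts' earlier albumin is thrown away altogether. On a visit-by-visit analysis those values still enter the earlier tests, and are only unused at the later ones. A reader might also treat this as independent of section 4.4. It is not: many patients who stop would fall under items 5 to 7, and all their values could then be removed, so a better model helps only if those patients remain in the analysis.

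It can also be said that confounding from self-selection is a larger threat than dropout. The mixed model does not remove that beyond admission albumin, but this is no reason to leave an avoidable second source of bias.

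**Conclusion.** The point holds in conditional form. The plan expects to lose a fifth of its patients, collects repeated albumin values that could largely correct for albumin-related loss, and specifies tests that do not use them. If dropout, or its relation to albumin, differs between the groups, the later comparisons can be biased in either direction. Under the stated assumptions and no true effect, the size runs from nothing, through an error that is small against 3.3 g/L, to a serious one only in the extreme case. Where in that range the trial will fall cannot be determined from the documents. The change should be made before analysis, because the data are already scheduled and the alternative is plainly better.

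**What to change.** - **Model.** In section 10, replace the separate albumin tests with one mixed model for repeated measures on all available postoperative values (day 6, months 1, 3 and 6). Include group, visit, group × visit and admission albumin × visit, with an unstructured covariance. Report the group difference with its 95% CI at each visit. Make the synopsis and section 3.2 agree.
- **Analysis set.** Define it as all enrolled patients with complete resection and pathologically confirmed hepatocellular carcinoma, which is consistent with inclusion criterion 2 and with items 1 and 4 of section 4.4.
- **Section 4.4.** Amend items 5 to 7 so that patients who withdraw or break the snack rules keep their albumin values collected up to that point in this analysis.
- **Sensitivity analysis.** Lower the assumed values of dropouts over a stated range, separately by group, because the model corrects only dropout that recorded values explain.

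The cost is SAP and protocol wording and somewhat more analysis code. The model runs in SPSS, which section 10 already names, but the sensitivity analysis normally needs imputation code as well. No new data are required. Confounding from the self-selected groups, beyond admission albumin, remains and needs its own handling.

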3.2 Experimental Steps

The specific steps of the study are as follows:

Pre-procedure preparation:

According to the literature research, establish the form of patients' clinicopathological data that need to be collected, including basic information (age, gender, hospitalization number), pre-surgical laboratory examination (nutritional indexes, liver function, renal function, coagulation function, blood routine, tumor markers such as alpha-fetoprotein, etc.), surgical records (tumor location, size, number, intra-operative bleeding, etc.), post-surgical laboratory examination, tumor recurrence and treatment modality and patient survival, etc., as well as the establishment of a dietary matching table, respectively writing the dietary education content of the experimental group and the control group, in order to personalize the guidance of the patient's postoperative diet and the correct understanding of the importance of dietary therapy. A case questionnaire was set up for the enrolled patients, and the relevant data of the enrolled patients were recorded in the form.

Screening and Trial:

Patients who were admitted to the Department of Hepatobiliary Pancreatic Surgery of Drum Tower Hospital affiliated to Nanjing University School of Medicine, from February 2024 to January 2025 and met the enrollment criteria were selected for inclusion in this study. The grouping was not randomized and blinded, and all patients were enrolled according to their individual wishes and divided into a test group (53 cases) and a control group (53 cases). The purpose of the study, the content of the investigation, the principle of confidentiality were explained to the patients or their families at the time of their admission to the hospital to reduce the concerns of the respondents, and the subjects were included in the study after signing the informed consent form with their consent.

1. Treatment program:

All patients were screened for nutritional risk using NRS 2002, nutritional assessment using PG-SGA, and malnutrition diagnosis using GLIM Malnutrition Assessment (Diagnosis) Criteria within 24h of admission. In accordance with the recommendations of ESPEN 2021 Practice Guidelines for Surgical Nutrition Therapy and CSPEN 2016 Guidelines for Perioperative Nutritional Support for Adults, the patients' daily target amount was set at 25-30 kcal/kg. In order to ensure the balanced dietary nutritional intake of the two groups, their standardized management was formulated as follows: ① Total calories: according to the patients' height, weight, age and activity Total calories: Calculate the daily intake according to the patient's height, weight, age and activity intensity, about 1200~2000 kcal. ② Carbohydrates: account for 60%~65% of the actual energy supply, calculate the actual supply of 180~325

g. The staple food is mainly cereals and potatoes. Protein: 1.2~1.5 g/kg/day according to the guideline, choose high quality protein, such as eggs, poultry, soybean products. ④Fat: account for 20% of the actual energy supply, calculate the actual supply of about 27~44 g. Distribute the energy of three meals as 30%, 40%, 30%. According to each patient's required intake, the corresponding nutritional program card is issued, and explained and emphasized at the time of admission and discharge, respectively. Patients could choose different food items on the cards according to their food preferences and actual situation. The experimental group was required to consume LES 1 h before bedtime, while the control group did not consume any food 1 h before bedtime.

Experimental group: patients were given additional meal (total calories 200-275kcal, protein 11.5g-18g, complex carbohydrates 25-55g) 1h before bedtime. the LES regimen was: ① whole protein type enteral nutrition; ② whey protein powder + bread or cookie. The addition of meals was carried out 1h before bedtime. The dietary regimen of the experimental group will be deducted from the corresponding late-evening snacks intake.

(1) Preoperative: ① Patients without nutritional risk: independent intake according to the issued diet program card. ② Patients with nutritional risk: daily oral whole-protein enteral nutrition on the basis of general diet after admission.

(2) Postoperative: start drinking small amount of water on the 1st postoperative day, over to liquid diet after ventilation, and may over to autonomous semi-liquid diet + oral whole protein enteral nutrition during the day + LES program on the 2nd postoperative day. As the patient's voluntary intake meets 60% of the body's needs, the daytime oral enteral nutrition support can be gradually stopped and the LES program can be continued.

3) Discharge: daily intake needs to be on time according to the LES regimen.

Control group: no more food 1h before bedtime.

(1) Preoperative: same as the test group.

(2) Postoperative: start drinking small amount of water on the 1st postoperative day, over to liquid diet after ventilation, and can over to autonomous semi-liquid diet + oral whole protein type enteral nutrition during the day on the 2nd postoperative day. As the patient's voluntary intake meets 60% of the body's needs, enteral nutrition support can be gradually stopped.

(3) Discharge: Doctors judge whether the patients need to continue nutritional support according to their dietary recovery, and if they do, their nutritional supplementation should be completed before 1h

before bedtime.

2. biological sample collection:

Serum samples remaining after testing were collected from patients for metabolomics analysis.

3.Clinical information collection:

(1) General information collection: gender, age, height, weight, BMI, ICG15min retention time, name of surgery, duration of surgery, blood loss, blood transfusion, tumor stage, NRS2002, PG-SGA, GLIM malnutrition assessment (diagnosis) criteria diagnosis;

(2) Nutritional indicators collection: collect nutritional indicators such as serum albumin (ALB), prealbumin (PA), transferrin (TRF), and total serum protein (TP) on the 1st day of the subject's admission to the hospital, on the 6th day of the postoperative period, at 1 month after the operation, at 3 months after the operation, and at 6 months after the operation.

(3) Collection of liver function indexes: Liver function indexes such as alanine aminotransferase (ALT), alanine grass aminotransferase (AST), γ -glutamyltransferase (GGT), cholinesterase (CHE), and total bilirubin (TBIL) were collected on the first day of hospitalization, the sixth postoperative day, the first postoperative month, the third postoperative month and the sixth postoperative month of the subjects.

(4) Clinical outcome collection: to collect clinical outcome indicators of subjects after surgery, such as: postoperative complication rate, recurrence rate, recurrence-free survival, quality of life.

5) Medical cost collection: to collect subjects' total hospitalization cost, cost of anti-infective drugs, cost of albumin during hospitalization.

Data analysis:

Descriptive statistics were performed on the clinical data, and the measures that conformed to normal distribution were expressed as mean \pm standard deviation ($\bar{x} \pm s$), and the t-test was used between the groups, and the measures that did not conform to normal distribution were expressed as median (interquartile spacing) [M(IQR)], and the Mann-Whitney U test was used between the groups. Count data were expressed as percentages [n(%)], and the chi-square test was used for between-group comparisons, with $P < 0.05$ considered statistically significant. The Kaplan-Meier method in STATA 12.0 was used to calculate the recurrence rate and recurrence-free survival in each group, and the log-rank test was used for intergroup comparison.

4. Case selection

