At the same time, the liver serves as the target organ for the metabolism of most nutrients, and the high metabolic status and organ invasion of cancer often expose liver cancer patients to malnutrition, with an incidence rate as high as 74.36% according to a survey ^[7]. In addition, hepatic resection will cause hepatocyte damage to a certain extent, resulting in the metabolic balance of sugar, protein, fat and hormones in the patient's body being disrupted, which makes the body's catabolism stronger than anabolism ^[8], and it is more likely to have a decrease in the level of albumin synthesis and a significant decrease in the intake of nutrients after the operation, which in turn results in the decrease in the patient's ability to resist infection, the increase in the risk of complications, and the decrease in the quality of life and a series of other poor prognosis ^[9,10,11,12], therefore, nutritional support and intervention are particularly important in this situation. According to our previous study, we found that nutritional intervention by clinical pharmacists in perioperative liver cancer hepatectomy patients could reduce the complication rate by 69%, as well as correct the inflammatory stress response and improve albumin levels more quickly ^[13].

Therefore, we believe that the use of rational and effective nutritional intervention strategies will bring positive benefits to patients.

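### No albumin or liver value is scheduled between hepatectomy and the written snack start on postoperative day 2, so in self-selected arms compared without adjustment an unequal surgical fall cannot be separated from the snack effect

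*Combined protocol and SAP*

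**What the plan says.** **Sampling.** Section 3.2 (Clinical information collection) takes albumin, prealbumin, transferrin and total protein "on the 1st day of the subject's admission to the hospital, on the 6th day of the postoperative period", then at 1, 3 and 6 months. Section 6.2 repeats this: values are "collected from subjects on day 1 of admission, day 6 postoperatively" and at the same later visits. Liver indices in section 3.2 "were collected on the first day of hospitalization, the sixth postoperative day, the first postoperative month" and at months 3 and 6; section 6.3 agrees.

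**Snack start.** The postoperative item for the test group in section 3.2 allows "oral whole protein enteral nutrition during the day + LES program on the 2nd postoperative day", and the synopsis says the same. The preoperative item mentions no snack, and the control group's preoperative care is stated to be identical. The general snack instruction in the synopsis (Treatment plan) and in section 3.2 (Treatment program) carries no start date.

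**Endpoint and sizing.** The primary indicator in section 7.1 is "Serum albumin (ALB), recording ALB data from patient biochemical tests", with no visit named. Section 3.1 sizes the trial on the expectation that "the albumin level before LES intervention was 34.2 ± 3.9 g/L", rising to 37.5 ± 5.4 g/L afterwards.

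**Allocation and analysis.** Section 3.1 describes open, non-randomised grouping by patient preference. Sections 3.2 (Data analysis) and 10 compare continuous measures between groups by t-test or Mann-Whitney test, without covariates. Section 3.2 collects type and length of operation, blood loss, transfusion, tumour stage and ICG retention, but no planned model uses them.

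**The concern.** Between the admission sample and a first snack on postoperative day 2 lie preoperative enteral nutrition in patients at nutritional risk, the hepatectomy itself, blood loss and transfusion. The plan expects the operation to matter: section 1 says that after resection "it is more likely to have a decrease in the level of albumin synthesis". The next scheduled value is on day 6, four days after the written snack start.

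If the two self-chosen arms differ in extent of resection, liver reserve or bleeding, their albumin may already differ before anyone has eaten a snack. Nothing in the schedule would show this, and nothing in the analysis would allow for it. Section 2.1 also makes recovery of liver function part of the primary purpose, yet no early postoperative value is scheduled from which recovery could be measured.

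**Working it through.** **Inputs.** Section 3.1 gives means of 34.2 and 37.5 g/L, SDs of 3.9 and 5.4 g/L, two-sided alpha 0.05, power 90%, 44 per group before dropout and 53 after. The plan gives no surgical fall, no difference in fall between arms and no within-patient correlation, so the imbalances below are assumptions shown as a range.

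**Step 1: reproduce the plan's figure.** Difference = 37.5 − 34.2 = 3.3 g/L. Pooled SD = √((3.9² + 5.4²)/2) = √22.185 = 4.71 g/L. By the normal formula, n per group = 2 × (1.960 + 1.282)² × 22.185 / 3.3² ≈ 42.8, so 43. Exact t-test power is 0.895 at 43 and 0.901 at 44. The stated 44 per group (88 in total) therefore reproduces.

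**Step 2: what the between-group test estimates.** Let A be the admission mean, F the surgical fall still present at the visit, and S the snack effect. Then:

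- test mean = A_T − F_T + S
- control mean = A_C − F_C
- difference = S + (A_T − A_C) − (F_T − F_C)

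If A and F are equal in the two arms, the difference is S whatever the size of F. A simulation with common falls of 0, 3 and 6 g/L agrees: the between-group difference stays at about 0 when S = 0 and at about 3.3 when S = 3.3. The change from admission within the test arm does move by the full fall: with S = 3.3 it is about +3.3, +0.3 and −2.7 g/L.

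Adjusting for admission albumin addresses A_T − A_C. It does not address F_T − F_C, which arises after that sample.

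**Step 3: size of an unequal fall.** SE = √((3.9² + 5.4²)/44) = √(44.37/44) = 1.00 g/L. For an imbalance d that persists to the visit, the false-positive rate with no snack effect is Φ(d/SE − 1.96) + Φ(−d/SE − 1.96). Power for a true 3.3 g/L when the test arm falls more is approximately Φ((3.3 − d)/SE − 1.96).

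| Assumed imbalance d (g/L) | False-positive rate, 44 per group | Power for 3.3 g/L if the test arm falls more, 44 per group | False-positive rate, 53 per group |
|---|---|---|---|
| 0 | 0.05 | 0.91 | 0.05 |
| 0.5 | 0.08 | 0.80 | 0.09 |
| 1 | 0.17 | 0.63 | 0.19 |
| 1.5 | 0.32 | 0.43 | 0.37 |
| 2 | 0.51 | 0.25 | 0.59 |

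The power column uses the normal approximation, hence 0.91 rather than the exact 0.901 in the first row. An imbalance of 1 g/L is 1/3.3 = 30% of the planned effect. More patients do not help: the false-positive rate is higher at 53 per group than at 44.

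No matching figures can be given for the liver indices, because the plan states no SDs for them.

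**The case against.** Two stronger readings are tempting, and the documents support neither. A reader might infer that there is no value before the intervention at all. There is: the admission sample precedes the snack as dated and is a usable baseline; only a postoperative pre-snack value is missing. A reader might also infer that the surgical fall itself will be taken for the snack's effect, or will hide it. Both arms undergo hepatectomy, are sampled at the same visits and are compared with each other, so a common fall cancels. No within-arm before-and-after test is planned.

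Other objections carry weight:

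- **This is mainly confounding.** Self-selection without adjustment creates the bias, and the surgical variables needed to reduce it are already collected. This stands, and adjustment therefore comes first in the fix. Those variables capture only the part of the fall that they predict, so a measured value still adds information.
- **The sizing figures need not be postoperative.** Section 3.1 takes its pre-snack albumin from literature and a pretest and does not say when it was measured. This stands; the sizing wording does not prove that a required value was omitted.
- **An early sample is imperfect.** It may reflect transfused products, and nothing in the plan says the fall is complete by day 2. This stands as a limitation.
- **Suitable blood may not already be drawn.** The liver-failure definition in section 7.2 applies from day 5 against the previous day, so it implies bilirubin and INR from about day 4 only. Section 3.2 lists postoperative laboratory tests without dates. This stands, so a free sample cannot be assumed.
- **The start date is not settled.** The undated instructions leave open that snacks begin before surgery. This stands and limits how the extra value may be used.

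**Conclusion.** The point holds in a limited form. If the snack starts on postoperative day 2 as dated, no albumin, prealbumin or liver value is scheduled between the operation and the first snack. In self-selected arms with unadjusted tests, a difference between arms in the surgical fall then passes one for one into the estimated snack effect at day 6 and possibly month 1. Whether this reaches the primary result depends on the visit used, which section 7.1 does not name. Recovery of liver function lacks a postoperative starting point.

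The false-positive rate runs from 5% with no imbalance to about 17% at 1 g/L and 51% at 2 g/L. These rates rest on the plan's SDs, 44 per group, and imbalances that are assumed and taken to persist to the visit. They show sensitivity; they are not evidence that such an imbalance will occur. The sample size of 88 is unaffected. The change is worth making because it is cheap.

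**What to change.** 1. **Adjust the analysis (sections 3.2 Data analysis and 10).** Replace the unadjusted comparisons of albumin and liver indices with ANCOVA or a mixed model for repeated visits. Adjust for the admission value and the surgical variables already collected: type of operation (grouped into a few prespecified classes), its length, blood loss, transfusion before the first snack, tumour stage and ICG retention. This needs no new data beyond the timing of transfusion.

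2. **Record one further value (sections 3.2, 6.2 and 6.3).** Take the last routine postoperative albumin and liver panel before the first postoperative snack, at the same postoperative time in controls. Use it as an additional covariate and as the starting point for recovery. The cost is one more data-entry point, and possibly an added assay if routine blood does not include it. State its limits: it may reflect transfused products or only part of the surgical fall.

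3. **Reconcile the snack start.** The undated instructions in the synopsis and in section 3.2 (Treatment program) must be reconciled by the sponsor with the postoperative items that name day 2. If any snack precedes surgery, the postoperative value is itself post-treatment and must not be a covariate. The admission value then remains the only baseline, and the plan should say so.
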